1. OVERVIEW AND OBJECTIVES

The **long-term objectives** of this research are to perform large-scale randomized clinical trials (RCT) with SISU mouth guards and SOVA night guards. Towards these long-term ends, the present proposal represents investigations into the most immediate issues that can be addressed in a preliminary study. The **outcome variables** for the present study fall into four categories: (1) fabrication efficacy, (2) compliance, (3) functional efficacy, and (4) user satisfaction. The **immediate goals of this preliminary proposal** will: (1) focus on the SOVA night guard, (2) conduct *in vivo* tests of the SOVA device under controlled clinical conditions, and (3) evaluate compliance and functional efficacy in the 'natural' environment of the patient's home. The clinical application involves protection of dental structures during nocturnal parafunction (sleep bruxism). Because of the potential co-morbidity of bruxism with temporomandibular disorders (TMD), a triad of masticatory myalgia, TM joint noises and/or joint arthritides, TMD signs and symptoms will be considered in future studies. **Future goals** will involve pursuing funding to perform large-scale RCT with both the SISU and SOVA night guards.

Specific Aim 1. Compare the SOVA night guard to the custom-acrylic bite splint in clinical laboratory conditions. Hypothesis: There will be no significant differences between the devices in terms of fabrication efficacy, functional efficacy or user satisfaction.

Specific Aim 2. Compare the SOVA night guard to the custom-acrylic bite splint under ecologically relevant conditions, i.e., the home environment. Hypothesis: There will be no significant differences between the devices in terms of compliance or functional efficacy.

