3. METHODS AND STUDY DESIGNS

3.1 Subjects. Sample size estimations (**Table 1**) are based upon a recent review of RCTs for bruxism management, in which acrylic appliances were evaluated (see Appendix 2 in (Huynh et al., 2007)). The mean \pm 1 SD number of bruxism episodes per hour with an occlusal splint (the gold standard) was 3.97 ± 0.58 , and for a palatal splint, the mean \pm 1 SD was 4.45 ± 0.63 . Using these means and the higher SD (0.63), along with an $\alpha = 0.05$ and $\beta = 0.8$, I determined that a study would be sufficiently powered with sample sizes of 29 per group. Based on other Michigan studies, I have estimated recruitment, exclusion and attrition rates, which suggest an estimated initial screening sample size of 120 necessary to end up with 29 per group (**Fig. 1**). There will be two treatment groups: a group receiving supervised training in the fabrication of the SOVA night guard (SOVA) and a group receiving the Michigan custom-acrylic bite splint (MI BS). Two groups times 29 subjects per group equals 58 total needed for analysis (**Fig. 1**, bottom).

Table 1. Treatment (Tx) groups & sample sizes (N).

[figure not shown]
Tx	SOVA	MI BS
N	29	29

Care will be taken to match the randomized groups for age, ethnicity, gender and TMD signs/symptoms. Alternatively these will be modeled as nuisance variables if attrition rates create bias and/or there is a lack of sufficiently sized screening pools. Subject inclusion criteria will be: (1) adults, male or female, (2) clinical signs of dental wear, (3) report from significant others of nocturnal grinding and clenching noises from potential subject, (4) absence of outstanding dental and medical conditions, including cardiovascular disease, sleep apnea, and diagnosed sleep disorders, (5) full dentition sans 3rd molars, (6) no movement or neurological disorders, (7) no active orthodontics, (8) no outstanding or previous periodontal problems, (9) no removable prostheses, (10) no medication use with movement disorders as known side effects, (11) ability to follow instructions, (12) ability to report to the clinical laboratory at appointed times over the course of the study. The presence or absence of TMD joint noises or masticatory myalgia will be permitted; however, joint arthritides will not be permitted.

3.2 Project design.

Fig. 2 provides an overview of the project flow. Each aspect will be described below.

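### Both aims rest on joint claims of no significant difference across several outcome families, with no primary outcome, primary visit or multiplicity rule, while the sample size covers only bruxism episodes per hour

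*Combined protocol and SAP*

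**What the plan says.** Section 1 states that the outcome variables "fall into four categories: (1) fabrication efficacy, (2) compliance, (3) functional efficacy, and (4) user satisfaction", without ranking them. Specific Aim 1, set in the clinical laboratory, has the hypothesis "There will be no significant differences between the devices in terms of fabrication efficacy, functional efficacy or user satisfaction". Specific Aim 2, set in the home, has the hypothesis "There will be no significant differences between the devices in terms of compliance or functional efficacy".

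Sections 3.2.4 to 3.2.8 fill these families:

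- **Fabrication:** four investigator-assessed aspects (stability, retention, tissue adaptation, tissue health) and a participant questionnaire.
- **Compliance:** a daily log, nocturnal EMG and microwear.
- **Functional efficacy:** two questions, one on bruxing activity and one on how the teeth and device hold up.
- **User satisfaction:** several questionnaires and single items.

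Section 3.2.9 schedules nearly all of these at 1 week and at 4 months. The analysis wording is ANOVA for tissue adaptation and repeated measures ANOVA for tissue health, each with an open alternative.

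Section 3.1 sizes the trial on bruxism episodes per hour alone. The rate "with an occlusal splint (the gold standard) was 3.97 ± 0.58"; for a palatal splint the mean and "SD was 4.45 ± 0.63". It concludes that the study is "sufficiently powered with sample sizes of 29 per group". It does not say at which visit this outcome would be compared.

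**The concern.** Each hypothesis is one statement about several outcomes, and statistical significance is the only criterion offered for it. Taken as written, one significant result on any measure at any visit contradicts the aim, and the chance of such a result between equal devices grows with the number of tests. The plan fixes neither that number nor which result decides, so the deciding outcome could be picked after the data are seen.

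There is also a risk in the other direction. Outside bruxism rate the plan gives no expected difference, no SD and no power, so an absence of significance on those outcomes carries no known assurance. At stake is whether either aim's conclusion, whichever way it falls, can be interpreted.

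**Working it through.** **1. Reproduce the sample size.** Inputs from Section 3.1: means 3.97 and 4.45, SD 0.63 (the larger of the two), alpha 0.05, and 0.8, which is labelled beta but only makes sense as power.

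- Difference = 4.45 − 3.97 = 0.48; standardized, 0.48 / 0.63 = 0.76.
- Normal approximation, two-sided: n = 2 × (1.960 + 0.842)² × (0.63 / 0.48)² ≈ 27.0, or 28 per group after rounding up.
- Two-sample t-test (noncentral t): power is 79.9% at 28 and 81.4% at 29, so 29 per group is needed.
- A one-sided test gives 22, and power of 0.2 gives 5. The plan's figure is therefore a two-sided test with 80% power, and it is correct for that one outcome.

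**2. Count the outcomes in each aim.** The plan gives no count of tests. Taking the outcomes named in Sections 3.2.5 to 3.2.8 and keeping the aims separate:

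- Aim 1 has three families. Listed out, these are stability, retention, tissue adaptation, tissue health, bruxing activity, wear of teeth and device, and satisfaction: seven outcomes.
- Aim 2 has two families. Listed out, these are compliance, bruxing activity, and wear of teeth and device: three outcomes.

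**3. Chance of at least one false difference.** With k independent tests at 0.05 and equal devices, this is 1 − 0.95^k.

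| Scenario | Aim 1 | Aim 2 |
|---|---|---|
| One test per family | k = 3: 14.3% | k = 2: 9.8% |
| Listed outcomes, one visit | k = 7: 30.2% | k = 3: 14.3% |
| Listed outcomes, two visits | k = 14: 51.2% | k = 6: 26.5% |

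**4. Effect of correlation.** With equally correlated normal test statistics, simulation for three tests gives 13.6% at correlation 0.3, 12.5% at 0.5 and 9.8% at 0.8. For 16 tests, slightly more than Aim 1's largest count, it gives 37.4% at 0.5 and 20.7% at 0.8. The excess over 5% shrinks but remains.

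**5. Power elsewhere at 29 per group.** Under a two-sided t-test at 0.05, 80% power requires a standardized difference of about 0.75. Power is about 46% at 0.5, 20% at 0.3 and 12% at 0.2.

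**6. Cost of keeping outcomes co-equal.** With Bonferroni control and the planning effect of 0.76, four tests (alpha 0.0125) have 63% power at 29 per group and need 41 per group for 80%. Eight tests (alpha 0.00625) have 53% power and need 46. With one primary, alpha stays at 0.05, n at 29 and power at about 81%.

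**The case against.** The strongest defence is that this is a preliminary study, described in Section 2 as a small RCT ahead of full-sized phase III trials, where several co-equal outcomes are easier to justify. The plan also states hypotheses, not an explicit rule that one significant result overturns an aim, and alpha 0.05 appears only in the sample size paragraph. Testing every outcome at 0.05 is therefore an assumption about how the hypotheses would be judged. This softens the point without removing it: Section 1 makes significance the stated criterion, Section 3.1 claims adequate power, and Section 3.2.9 looks ahead to publications and further proposals.

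Doubling the count for two visits is also an assumption. A repeated measures ANOVA is named for tissue health and could merge visits for other outcomes too. Subjective fabrication is assessed only at Step 2. Compliance and functional efficacy share EMG and microwear data, so independence will not hold. All this stands, and is why a range is given.

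A reader might go further and infer that the hypotheses fail or hold largely by chance, pooling eight outcomes for 1 − 0.95^8 = 33.7%, or sixteen outcome-visits for 1 − 0.95^16 = 56.0%. The documents do not support this. Neither aim contains all eight outcomes: compliance belongs only to Aim 2, and fabrication and satisfaction only to Aim 1. Those figures also need independence and one test per visit. And if a hypothesis holds despite a real difference, the cause is limited power together with reading non-significance as equality, not chance alone.

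**Conclusion.** The concern holds in a bounded form. The plan names no primary outcome, no primary visit and no multiplicity rule, and it sizes the trial for one measure within one of four families. If each outcome is tested at 0.05, equal devices would show at least one difference with probability 14% to 51% for Aim 1 and 10% to 26% for Aim 2. The lower ends assume one test per family and the upper ends all listed outcomes at two visits, all under independence. Positive correlation or merged visits bring the figures down, though every case computed stays above 5%. Outside bruxism rate, an absence of significance has no stated power behind it, and a moderate standardized difference of 0.5 would be missed more often than found. The gap is therefore more than a missing label, but the sample size arithmetic is sound.

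**What to change.** Name bruxism episodes per hour, the outcome behind the calculation in Section 3.1, as the single primary outcome at one pre-specified visit. Four months is a reasonable choice, but it is a recommendation, since the plan ties the sizing to no visit. Rest the Aim 2 conclusion on this outcome.

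Keep Aim 1's own laboratory, fabrication and satisfaction outcomes. Resting Aim 1 on a sleep measure taken at home would remove the question it asks. Label these, all other outcomes and the non-primary visit (1 week, if 4 months is chosen) as secondary, and report them as between-group estimates with 95% confidence intervals.

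Apply any Holm adjustment only to claims of a difference. The investigator hopes for non-significance, and adjustment makes that easier to reach, so it must not be used to support similarity. State that no non-significant result, adjusted or not, will be read as similarity. This applies to the primary too: naming it does not supply an equivalence margin, which is a separate matter.

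The cost is protocol wording, with no change to the 29 per group or to power of about 81% for the primary. The downside is that secondary outcomes lose unadjusted significance claims and Aim 1 becomes descriptive.

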The issue with custom-made hard acrylic appliances is that they are expensive and cannot be repetitively covered by insurance. Hence, there is a need for an inexpensive, reliable and replaceable alternative that has the functional efficacy of the custom hard acrylic appliances. It is also clear that, for such a device to be a legitimate alternative, it must undergo the appropriate clinical trials (ADA report. Using mouthguards to reduce the incidence and severity of sports-related oral injuries., 2006; Centers for Disease Control and Prevention. Promoting oral health: interventions for preventing dental caries, oral and pharyngeal

cancers, and sports-related craniofacial injuries. A report on recommendations of the task force on community preventive services., 2001; Friction et al., 2010).

Planned studies will escalate as follows. The initial studies will involve performing a small RCT with 29 subjects in two groups (below). Subsequent future research will involve full-sized phase III trials of the SOVA night guard, while simultaneously developing a jaw function simulator. The technologies and insights developed from the simulator and phase III trials will provide solid methods for successful phase IV SOVA trials. Subsequently, the advances made with the SOVA studies will provide the necessary means for conducting phase III and IV trials of the SISU mouth guard device, which will take place under the hostile conditions attending contact sports. Of course, additional IRB approvals and funding will be required to pursue these future objectives.

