3.2.5a. Stability and retention will be quantitatively assessed with jaw movement (custom jaw tracking devices in conjunction with a MaxTraq motion analysis system [Innovision, Columbiaville, MI] and EMG [LabChart, ADInstruments, Colorado Springs, CO] data) and force sensors (T-scan, Tektronix, South Boston, MA). For position-stability assessment, maxilla, mandible and the splint will be simultaneously recorded from at least three sites each (to capture 6 degrees of movement freedom). Subjects will clench, grind, perform closed border movements and vacuous chewing (verified with EMG and force sensors). For retention assessment, subjects will perform a series of tests designed to dislodge the device, e.g., tapping, forced blowing, coughing, chewing on gum. Stability and retention indices will be created based on whether device movements vary independently of jaw movements and applied bite forces, and how force sensor output varies during dislodgement exercises. (Note, the force sensors will be placed between the device and the maxilla, so that reductions in sensor output will indicate that the device is being dislodged.) Deviations will be used to form standardized indices of stability and retention, with smaller values representing greater stability and retention.

3.2.5b. Tissue adaptation will be assessed by using a 3D laser scanner. The occlusal, facial and lingual surfaces of the upper arch will be scanned as will the inner surface of the night guards. An index of

[figure not shown]

Fig. 2. Overview of planned studies (see text).

adaptation will be developed based on the volumetric spaces separating the teeth from the device, using topological software. Smaller volumes will represent better tissue adaptation. Volumetric indices will be compared between devices via ANOVA or appropriate statistical methods.

3.2.5c Tissue health will be assessed via appropriate, standard methods currently used in cariology and periodontology clinical studies (Monse et al., 2012; Tirapellia et al., 2010). Baseline measurements will be compared with post-device wear measurements. Between-group differences will be studied with a repeated measures ANOVA or appropriate statistical methods.

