Table 2. Summary of objectives, methods and when performed		
Assessment	Method or modality (equipment)	When
Subjective fabrication	Questionnaires (na)	Step 2
Stability	Performance during jaw function, bite force and muscle use (MaxTraq + EMG + T-Scan)	Steps 2, 4, 5
Retention	Shape conformity (3-D laser scanner, topology)	Steps 4,5
Tissue adaptation	Tooth wear and gingival health (standard dental)	Steps 4,5,6
Tissue health		
Compliance	Self-report (questionnaires), Evidence of nocturnal use (EMG-sleep + microwear)	
Functional efficacy	Bruxism/TMD evidence, dental changes (EMG-sleep + 3-D scanning + microwear)	
User satisfaction	Questionnaires (na)	

3.2.9 Repeated measures (Step 4 Week 1 check-up and Step 5 4 Month check-up). Compliance, stability, retention, tissue adaptation and health, functional efficacy and user satisfaction will be assessed two times, viz., 1 week after delivery and 4 months after delivery (Fig. 2, Table 2). This will provide a

rigorous data set, reduce subject attrition and thus allow for both publications and further proposal applications to be pursued.

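### Both aims hypothesise no significant difference between the devices, with no margin or confidence-interval criterion; at 29 per group a non-significant result cannot show that SOVA matches the custom splint.

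*Combined protocol and SAP*

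**What the plan says.** Section 1 states the hypothesis of Specific Aim 1 as "There will be no significant differences between the devices in terms of fabrication efficacy, functional efficacy or user satisfaction" and that of Specific Aim 2 as "There will be no significant differences between the devices in terms of compliance or functional efficacy". Section 2 gives the motive: "there is a need for an inexpensive, reliable and replaceable alternative that has the functional efficacy of the custom hard acrylic appliances".

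Section 3.1 takes two reference means from a published review of bruxism treatments. The bruxism episode rate per hour "with an occlusal splint (the gold standard) was 3.97 ± 0.58", and with a palatal splint it was 4.45 ± 0.63. From these means and the larger SD the plan concludes: "I determined that a study would be sufficiently powered with sample sizes of 29 per group".

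Tests are named in two places only. For tissue adaptation (Section 3.2.5b): "Volumetric indices will be compared between devices via ANOVA or appropriate statistical methods". For tissue health (Section 3.2.5c): "Between-group differences will be studied with a repeated measures ANOVA or appropriate statistical methods". Section 3.2.7, on functional efficacy, names no test for bruxism episodes. No section gives an equivalence or non-inferiority margin, a confidence-interval criterion, or a rule for concluding that the devices are alike.

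**The concern.** When the research hypothesis is the absence of a significant difference, failing to reject confirms it. Small numbers, noisy measurement and dropout then all work in its favour. The sample size protects against missing a difference of 0.48 episodes/h. It sets no limit on how much worse SOVA may be and still count as matching.

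The plan writes no explicit decision rule, so the reading of a null result is inferred from how the hypotheses are worded. What depends on it is the central question of Section 2: whether a cheaper device does the job of the acrylic splint. Section 3.2.9 says the repeated assessments will "thus allow for both publications and further proposal applications to be pursued", so a null result misread as similarity would carry into print and into the planning of the later trials.

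Fabrication efficacy, compliance and user satisfaction carry the same hypothesis but have no sample-size basis at all, so a non-significant result there says less still.

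**Working it through.** **Inputs (Section 3.1).** Means 3.97 and 4.45 episodes/h, so the gap is 4.45 − 3.97 = 0.48 (derived; the plan does not print it). SD 0.63, n = 29 per group, α = 0.05. The plan writes β = 0.8, which must mean power 0.80 to give 29. Sidedness and test are not stated. A positive difference (SOVA minus MI BS) means SOVA is worse.

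**Reproducing the plan's 29.** Normal approximation, two-sided: n = 2 × [0.63 × (1.960 + 0.842) / 0.48]² = 27.04, rounded up to 28. The t-test solution is 28.04, rounded up to 29. Power by t-test is 79.9% at 28 per group and 81.4% at 29. Other readings do not give 29: one-sided with SD 0.63 gives 22 to 23, and two-sided with SD 0.58 gives 23 to 24. So 29 is the size for a two-sided difference test, and that test is used below.

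**Precision at 29 per group.**
- SE = 0.63 × √(2/29) = 0.1654
- t(0.975, 56 df) = 2.003
- Expected 95% interval half-width = 2.003 × 0.1654 = 0.331
- Upper limit for a just-non-significant result = 2 × 0.331 = 0.663
- The interval still includes 0.48 when the observed excess is at least 0.48 − 0.331 = 0.149. So any observed excess from about 0.15 to 0.33 is non-significant and yet compatible with the whole gap between the two reference splints.

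**Chance of a non-significant result (noncentral t).**

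| True SOVA excess (episodes/h) | P(non-significant) |
|---|---|
| 0.20 | 78% |
| 0.24 | 70% |
| 0.30 | 57% |
| 0.40 | 34% |
| 0.48 | 19% |

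The plan sets no threshold; 0.24 is half of its gap, used for illustration.

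**Non-significant with an interval that includes 0.48 (simulation).** If SOVA is truly 0.24 worse, this happens in 41% of trials, which is 58% of the non-significant ones. If the devices are truly equal, it happens in 16% of trials, or 17% of the non-significant ones.

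**What a non-inferiority criterion would require.** The margins are assumptions, since the plan gives none. The criterion is that the upper limit of the two-sided 95% interval lies below the margin m, with truly equal devices. Power = P[T(56 df, noncentrality m/SE) > 2.003].

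| Margin m | m/SE | Power at 29 per group | n per group for 80% power |
|---|---|---|---|
| 0.48 | 2.90 | 81% | 29 |
| 0.36 | 2.18 | 57% | 50 |
| 0.24 | 1.45 | 30% | 110 |

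The normal approximation gives 28, 49 and 109 per group.

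No such figures can be given for the other outcomes, because the plan states no SD or target for them.

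**The case against.** The strongest reply is that the error is predicted rather than written. The aims are to compare the devices, and the hypothesis lines can be read as conventional nulls. On that reading Section 3.1 is coherent: 29 per group gives about 81% power to reject at 0.48. Section 2 speaks of a general need and places full-sized phase III trials after this small study, so it does not plainly assign the matching claim to this trial. It stands that no decision rule is written and that the study calls itself preliminary; both lower the stakes. But each line is labelled as the hypothesis, no alternative is given, and even a formal null that is not rejected gives no support for the need stated in Section 2.

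A second reply is that the figures rest on choices the plan does not make. This is partly right. The plan never calls 0.48 a tolerable deficit, 0.24 is illustrative, and the t-test is inferred. Covariate modelling (allowed in Section 3.1) or use of both the 1-week and 4-month assessments could change the 0.33 half-width. With truly equal devices the misleading pattern arises in 16% of trials rather than 41%. None of this supplies the missing criterion.

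A third reply is that 29 per group is adequate for a margin of 0.48. The arithmetic is correct, so the fault is the missing criterion and not necessarily the number of subjects. But 0.48 is the full gap between the two reference splints, and the plan does not offer it as a margin.

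Finally, the missing sizing for other outcomes and the missing test for bruxism episodes are separate gaps. They would remain after the rewording proposed here.

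**Conclusion.** The concern holds. Both aims state a hypothesis that p>0.05 would satisfy, in a study sized only to detect a difference, and nothing in the plan limits how large a deficit may remain compatible with the data. For bruxism episodes/h the comparison would miss a true deficit of 0.48 about one time in five and one of 0.24 about seven times in ten. A non-significant result can carry an interval reaching about 0.66.

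These figures assume SD 0.63, 29 analysed per group and a two-sided t-test at 0.05 on a single comparison. They apply to no other outcome. The point should be fixed: the inference is invalid under both aims and cheap to correct, although the study's preliminary status limits the harm.

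**What to change.** In Section 1, replace both hypotheses with wording such as:

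> For each outcome we will estimate the SOVA minus MI BS difference with its 95% confidence interval. A p-value above 0.05 will not be read as equality or as matching efficacy.

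In Section 3.1, add that 29 per group gives an expected 95% interval half-width of about 0.33 episodes/h at SD 0.63, for a simple two-group comparison. No margin is needed for this.

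Only if the sponsor wants to claim that SOVA is not worse should the plan state and justify a margin for bruxism episodes/h in advance and judge the upper limit of the two-sided 95% interval against it. It should then report the power at 29 per group with truly equal devices: about 81% at 0.48 (the whole reference gap, so hard to justify), 57% at 0.36 and 30% at 0.24. The outcome and time point for such a claim are the sponsor's choice.

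**Cost.** The estimation wording needs no extra subjects or visits; its downside is that a wide interval can no longer be presented as success. A not-worse claim at a margin tighter than 0.48 does cost subjects: for 80% power, about 50 per group at 0.36 and 110 per group at 0.24, against 29 planned.
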